5.4.3.3 Number of new or enlarging T2 lesions

New or enlarging T2 lesions as compared to the previous scheduled visit are recorded by the external reader in two distinct categories: ‘Number of new or enlarging T2 lesions without Gad. enhancement on T1’ (T2New_R) and ‘Number of new or enlarging T2 lesions with Gad. enhancement on T1’ (T2NewGd_R) at a visit as compared to the previous scheduled visit. The sum of both is the ‘number of new or enlarging T2 lesions’ at that visit compared to the previous scheduled visit. For subjects with missing baseline MRI, the number of new or enlarging T2 lesions from baseline cannot be assessed and the endpoint is considered missing. The baseline MRI is considered missing if presence of T1 Gd+ lesions at baseline is missing.

The cumulative number of new or enlarging T2 lesions from baseline to Week 24, Week 48, Week 72, Week 96, EOT and EOS is calculated as the sum of lesions at all post-baseline MRI visits up to the applicable MRI visit.

The cumulative number of new or enlarging T2 lesions from baseline up to the applicable MRI visit is derived as the sum of the ‘number of new or enlarging T2 lesions’ at all scheduled post-baseline MRI visits, including premature EOT visit if applicable (irrespectively if a visit is conducted during PTOP or not), for subjects with only scheduled post-baseline MRI scans.

For subjects with at least one unscheduled post-baseline MRI scan, care needs to be taken in the derivation to avoid double counting of lesions and the following algorithm applies:

- If a subject has an unscheduled MRI which is the last available MRI in the time period considered: Include that last unscheduled MRI when summing over ‘number of new or enlarging T2 lesions’ in the same way as the scheduled visits.
- If a subject has an unscheduled MRI which is not the last available MRI for the subject in the time period considered: Do not include that unscheduled MRI. Rationale: New / enlarging lesions at the unscheduled MRI as well as at the later scheduled MRI are reported in reference to the previous scheduled visit. Including both would result in double counting.

To account for varying observation time the analysis will be adjusted by: Time up to the last MRI (years) = Date of last MRI considered in derivation – Randomization date + 1 divided by 365.25 days.

Rationale: The number of T2 lesions is expected to increase with observation time, not solely by the ‘Number of MRI scans’. Therefore, adjustment by observation time is conducted. As in this study an additional MRI following premature treatment discontinuation is scheduled, the ‘number of MRI scans’ is not necessarily expected to be a good approximation of the observation time.

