5.4.2.3 Number of combined unique active lesions (CUAL) up to EOS

The cumulative number of CUAL from baseline to EOS is calculated as the sum of new T1 Gd+ lesions and new or enlarging T2 lesions without Gd enhancement on T1 at all post-baseline MRI visits up to EOS.

MRI scans are scheduled at Baseline, and every 24 weeks thereafter, i.e., at the visits at Week 24, Week 48, Week 72, Week 96, Week 120, Week 144 Visit and at the EOT visit. For subjects who prematurely discontinue treatment, an additional premature EOT visit MRI is scheduled. Unscheduled MRI scans may be conducted in addition.

MRI data are read centrally and provided to the sponsor.

To account for varying observation time, e.g., in case of premature study withdrawal or missing MRI assessments, the analysis will be adjusted by: Time up to the last MRI (years) = (Date of last MRI considered in derivation of CUAL – Randomization date + 1) / 365.25 days.

Rationale: Due to the fact that MRI scans are scheduled every 24 weeks, the CUAL count is expected to be mainly driven by new T2 lesions. The number of T2 lesions is expected to increase with observation time. In contrast, in studies where MRI scans are scheduled more regularly, the CUAL count is mainly driven by new T1 Gd+ lesions which are expected to increase with the ‘Number of MRI scans’ conducted. Also, in this study, there is an additional MRI following premature treatment discontinuation which can occur at any time, and which does not occur per

the planned schedule for any subjects and so the ‘number of MRI scans’ is not necessarily expected to be a good approximation of the observation time.

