5.4.2.3.1 Derivation details

The central reader provides the ‘Number of new T1 Gd+ enhancing lesions’ (variable T1GdNew_R) and ‘Number of new T2 lesions without Gd enhancement’ (variable T2New_R) at a visit as compared to the last scheduled MRI scan (with premature EOT visit being considered a scheduled MRI). At the first scheduled post-baseline visit comparison is made to baseline (with baseline defined as the Baseline Visit 2, or Visit 2 - 2nd attempt if available [see Section 5.4.3] for details and a rationale).

Cumulative CUAL from baseline to EOS is derived as the sum of ‘Number of new T1 Gd+ enhancing lesions’ and ‘Number of new T2 lesions without Gd enhancement on T1’ across all post-baseline MRI visits up to up to EOS irrespective of whether a visit is conducted during PTOP or not.

As only the number of new lesions as compared to the last scheduled visit is recorded by the central reader, lesions are not expected to be double counted when summing over scheduled visits.

In the rare event that the baseline MRI visit is conducted after randomization date, the variable is derived in the same way, i.e., based on the nominal visit. Note that effectively the derived variable then covers a period starting slightly after randomization. If the baseline MRI is missing, new or enlarging T2 lesions as compared to baseline cannot be assessed and consequently the endpoint is considered missing. The baseline MRI is considered missing if presence of T1 Gd+ lesions at baseline is missing.

For subjects with at least one unscheduled post-baseline MRI scan, care needs to be taken in the derivation to avoid double counting of lesions and the following algorithm applies:

- If a subject has an unscheduled MRI which is the last available MRI in the time period considered: Include that last unscheduled MRI when deriving CUAL in the same way as for scheduled visits.
- If a subject has an unscheduled MRI which is not the last available MRI for the subject: Do not include that unscheduled MRI. Rationale: New / enlarging lesions at the unscheduled MRI as well as at the later scheduled MRI are reported in reference to the previous scheduled visit. Including both may result in double counting.

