5.4.3.2 Number of T1 Gd+ lesions

The **number of T1 Gd+ lesions per visit** is derived as the sum of ‘number of new T1 Gad.-enhancing lesions’ (T1GdNew_R) + ‘number of persisting T1 Gad.-enhancing lesions’ (T1Gd_R) as provided by the central reader at that visit.

Handling of missing MRI results at scheduled visits follows the general rules for MRI data described in Section 5.4.3 above.

The **cumulative number of new T1 Gd+ lesions from baseline to Week 48** is derived as the sum of number of **new** T1 Gd+ lesions at all post-baseline MRI scans up to the Week 48 MRI visit. This includes premature EOT scans if available. It may include unscheduled scans if it is the last available scan, following selection of unscheduled MRIs as per derivation of CUAL [Section 5.4.2.3]. To account for a potentially varying number of scans contributing to the variable, the analysis will be adjusted by the ‘Number of MRI scans’ included in the derivation.

Note: The number of T1 Gd+ lesions at baseline is taken from the variable ‘Number of T1 Gad.-enhancing lesions at V2 – Baseline/Number of persisting T1 Gad.-enhancing lesions’ (T1Gd_R). At baseline new T1 Gd+ lesions are not available, thus no corresponding record is expected.

Note: T1 Gd+ lesions are assumed to not enhance for more than 12 weeks. This requires handling of data as follows:

- *If at a visit, number of persisting T1 Gd+ lesions are not recorded, the number of Gd+T1 lesions is the number of new T1 Gd+ lesions. Rationale: As per central reader processes*

persisting T1 Gd+ lesions are not assessed for subjects with scheduled MRIs scheduled more than 12 weeks apart (i.e., MRIs are scheduled every 24 weeks).

- *If at a MRI scan which is > 12 weeks (84 days) since the last previous scheduled MRI scan a persisting lesion count > 0 is recorded, these persisting lesions are considered implausible and therefore not to be considered in derivations of total T1 Gd+ counts.*

The cumulative number of new T1 Gd+ lesions from baseline will also be derived in the same way as described above for cumulative up to Week 48 for the following timepoints: Week 24, Week 72, Week 96, and EOT and EOS.

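### SAP 5.4.3.3 decides whether the baseline for new/enlarging T2 lesions is missing from the gadolinium result, which the T2 count does not use

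*SAP*

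**What the plan says.** For the T2 endpoint (SAP 5.4.3.3), a subject without a baseline MRI has no result: "the number of new or enlarging T2 lesions from baseline cannot be assessed and the endpoint is considered missing". The next sentence says how absence is recognised: "The baseline MRI is considered missing if presence of T1 Gd+ lesions at baseline is missing".

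For CUAL (SAP 5.4.2.3.1) the same test is used, and the reason given is again about T2: "If the baseline MRI is missing, new or enlarging T2 lesions as compared to baseline cannot be assessed and consequently the endpoint is considered missing". CUAL itself is "calculated as the sum of new T1 Gd+ lesions and new or enlarging T2 lesions without Gd enhancement on T1" (5.4.2.3). The central reader reports both components "at a visit as compared to the last scheduled MRI scan", and "At the first scheduled post-baseline visit comparison is made to baseline".

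SAP 5.4.3.2 adds two statements about gadolinium: "T1 Gd+ lesions are assumed to not enhance for more than 12 weeks", and, under the central reader's processes, "persisting T1 Gd+ lesions are not assessed for subjects with scheduled MRIs scheduled more than 12 weeks apart".

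**The concern.** The stated reason for setting the endpoint to missing is that T2 change cannot be judged without a baseline. Whether it can be judged depends on the baseline T2 image. The SAP instead looks at whether a result from the post-contrast T1 sequence exists. If the two sequences can be available independently, the rule can be wrong in both directions: a valid count is thrown away, or a subject with no T2 reference stays in the model. At stake are the T2 analyses at every timepoint (9.8.3) and, to a lesser degree, the CUAL analyses (9.7.3 and the first 9.8.1), in a trial that stopped with 136 randomized subjects.

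**Working it through.** The SAP gives no figure on this point, so there is none to reproduce. The check is to trace which baseline measurement each count uses.

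**1. T2 endpoint (5.4.3.3).** The count at a visit is T2New_R + T2NewGd_R, both read against the previous scheduled scan. The two parts differ only in whether the lesion enhances at that visit, and adding them removes the distinction. Baseline enhancement enters neither part. The only baseline input is the T2 image.

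**2. Can the two baseline results differ?** SAP 5.2.2 lists presence of T1 Gd+ lesions and T2 lesion volume on the baseline scan as separate central-reader variables. In Attachment 1, section 1.2, deviation code PD_MM.302 foresees pre-randomization MRIs with missing sequences. So the plan allows for one sequence to be present without the other.

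**3. What the rule does in each case.**

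| Baseline T2 | Baseline Gd | SAP rule | What the T2 count needs |
|---|---|---|---|
| readable | present | keep | keep |
| readable | missing | set to missing | keep |
| unusable | present | keep | set to missing |
| unusable | missing | set to missing | set to missing |

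The rule errs in rows 2 and 3.

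**4. Row 3 and the offset.** The offset is the time from randomization to the last MRI used. Take scans at Weeks 24 and 48 (nominal Days 169 and 337, Table 7), with treatment starting on the day of randomization. Suppose no Week 24 T2 count can be made and the sum simply skips it.
- Offset: 337 / 365.25 = 0.923 years.
- Time actually covered by the count: (337 − 169) / 365.25 = 0.460 years.
- Ratio: 0.460 / 0.923 = 0.50.

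That subject's rate would be understated by about half. This illustration rests on an assumption about what the reader delivers, which the SAP does not state.

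**5. CUAL (5.4.2.3, 5.4.2.3.1).** One component, T1GdNew_R, is read against baseline at the first scheduled post-baseline scan, so the baseline gadolinium image is a stated reference.
- First scan at Week 24: 24 weeks exceeds the assumed 12-week limit on enhancement, and 5.4.3.2 treats persisting lesions beyond 84 days (12 × 7) as implausible. Enhancing lesions are then in effect all new, whatever the baseline result.
- First scan is an early premature EOT scan: it counts as scheduled (5.4.2.3.1) and can occur at any time (5.4.2.3). Within 84 days of baseline, the baseline result bears on which lesions are new.

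By contrast, the cumulative new T1 Gd+ endpoint in 5.4.3.2 sums the same T1GdNew_R values, and neither 5.4.3.2 nor the general MRI rules in 5.4.3 set it to missing when the baseline gadolinium result is absent.

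**6. Size.** One subject is 1 / 136 = 0.7% of those randomized. The share in row 2 is not given. As pure assumptions:
- 0%: 0 subjects
- 1%: 0.01 × 136 = 1.4
- 3%: 0.03 × 136 = 4.1
- 5%: 0.05 × 136 = 6.8

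**The case against.** The strongest defence is that requiring a complete baseline scan is a simple, pre-specified rule, applied alike to both arms and normally resting on a pre-randomization value. It gives no evident route to differential bias. The situation should also be uncommon. Attachment 1 expects the central quality review to be considered before randomization (PD_MM.050), failure to repeat a deficient scan is an important deviation (PD_MM.302), and a second-attempt baseline scan replaces the first where it exists (5.4.3). Nothing in the SAP shows that the reader would deliver T2 counts when baseline gadolinium is missing, or that any such subject exists. T2 lesion volume would itself be only an indicator of a usable T2 reference.

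A reader might also infer that neither endpoint needs the baseline gadolinium result. That does not hold for CUAL, because its T1 Gd+ component is read against baseline at the first scheduled post-baseline scan. Early first scans are plausible: after the termination decision, subjects on treatment were to have their EOT visit within 8 weeks (section 2). Dropping the gadolinium requirement for CUAL altogether could count lesions already enhancing at baseline as new.

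All of this stands as to the size of the problem and as to CUAL. It does not rescue the T2 rule, whose own stated reason concerns T2 while its test does not.

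**Conclusion.** The point holds for the new/enlarging T2 endpoint: the missing-baseline test in 5.4.3.3 uses a measurement that the count does not need and overlooks the one it does. For CUAL it holds only in part. The T2 reading is needed there too, and the gadolinium result is needed only when the first scheduled post-baseline scan comes within 84 days of baseline; this rests on the SAP's own 12-week assumption.

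The documents do not support saying that subjects are in fact being dropped. The number with one baseline sequence and not the other is unstated and may be zero, and the 0 to about 7 subjects above is an assumed range. The primary endpoint is untouched, the secondary analyses are declared exploratory (9.1.1, 9.7), and the T2 variable is itself exploratory (5.4.3). This is a minor correction, worth making because it costs little.

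**What to change.** - **5.4.3.3:** treat the baseline as missing when the baseline T2 reading used as the reference for lesion counts is missing, for example when there is no centrally read baseline T2 result. Confirm with the central reader which delivered variable best shows that the T2 image was usable.
- **5.4.2.3.1:** require the same baseline T2 reading. Require the baseline T1 Gd+ result in addition only when the first scheduled post-baseline scan, including a premature EOT scan, is within 84 days of the baseline scan. Refer to the 12-week assumption in 5.4.3.2.

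The cost is a few sentences and slightly more derivation work, chiefly the check on scan dates for CUAL. No new data are needed.

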5.4.4 Other clinical efficacy variables

5.4.4.1 Time to 24-week CDA

The derivation of the variables for Time to 24-week CDA up to EOS follows the same approach as described in Section 5.4.2.1, but onset of progression is to be confirmed after 24 weeks (≥ 154 days, i.e., 168 days – two times 7-day visit time window) instead of after 12 weeks. The progression has to be persistent between onset and confirmation.

5.4.4.2 Change in EDSS from baseline by visit up to EOS

Absolute changes from baseline in EDSS score by visit are derived, based on the overall EDSS score as reported by the investigator in the eCRF. For subjects prematurely discontinuing treatment, results collected during PTOP are considered at the corresponding nominal visit in the same way as for subjects completing treatment as planned (e.g., by visit analysis at Week 24, considers both ‘Week 24’ and ‘PTOP Week 24’ visits). Baseline EDSS is defined as in Section 5.4.2.1.

On-treatment EDSS assessments will be flagged, i.e., EDSS assessments performed after study treatment start (date/time) and prior to EOT + 7 days.

5.5 Safety variables

5.5.1 Definition of treatment-emergent, baseline and change-from-baseline, last on treatment, follow-up assessments for safety variables

For all safety data analyses described in this SAP, baseline is considered to be the last valid assessment prior to first study drug intake. Assessments at Visit 1 (Screening) and Visit 2 (Baseline), with date on or prior to the date of first intake of study treatment, and with no time collected, are considered eligible for baseline.

For each individual safety variable, baseline is defined to be the last valid measurement available before the date and time of first dose intake of study treatment, unless otherwise specified. On days where study drug is initiated or re-initiated, the pre-dose assessment for that day is defined as the last non-missing assessment prior to the study drug intake on that day. The pre-dose assessment on Day 1 (if available) is identical to baseline; however, missing pre-dose data on Day 1 is not imputed with baseline. In case of (partially) missing assessment dates/times, or for assessments reported on Day 1 (or day of re-initiation) with recorded assessment time contradicting the timepoint label (e.g., pre-dose, 2 hours post-dose), the nominal visit and timepoint labels will be used to determine whether an assessment is considered for baseline (for example a blood pressure measurement with an assessment date on Day 1 but with a missing assessment time or an assessment time prior to the reported time of first study drug intake, will not be considered for

baseline if reported under the timepoint “2 hours post-dose” in the eCRF, however it will be considered if reported as “Pre-dose” in the eCRF).

Absolute changes from baseline are defined as post-baseline value minus baseline value, i.e., a positive sign indicates an increase compared to baseline.

A percentage change from baseline is defined as the absolute change from baseline divided by the baseline value (if the baseline value is > 0) and then multiplied by 100.

Absolute and percent change from baseline is calculated and stored for all continuous safety data.

In addition, the following assessments are flagged or derived per parameter:

- Last on-treatment assessment: Last assessment prior to or on EOT date +1 day (last on treatment may come from a scheduled or an unscheduled visit)
- Day-30 follow-up, between EOT + 16 days and EOT + 37 days [see Section 11.4]

A safety assessment (ECG, vital signs, laboratory) is considered treatment-emergent, if the assessment date is on or after the study treatment start date and prior to or on the study treatment end date + 15 days (inclusive). If both, the assessment date/time and the date/time of study treatment start are available, only events with date/time on or after the date/time of study treatment start are considered to be treatment-emergent. In case of (partially) missing assessment dates/times, or for assessments on treatment Day 1 with reported assessment time contradicting the timepoint label, the nominal visit and timepoint labels will be used to determine whether an assessment is considered as treatment-emergent or not. For example, a blood pressure measurement with an assessment date on Day 1 but a missing assessment time or an assessment time after the time of first study drug intake, will not be considered treatment-emergent if reported under the timepoint “Pre-dose” in the eCRF, however it will be considered if reported as “2 hours post-dose” in the eCRF.

A safety event (AE, serious AE [SAE], Death) is considered treatment-emergent if the onset date/date of occurrence is on or after the study treatment start date and prior to or on the EOT date + 15 days (inclusive). Missing or partially missing onset or occurrence dates are imputed as described in Section 12.3. If both the onset/occurrence date/time and the date/time of study treatment start are available, only events with date/time on or after the date/time of study treatment start are considered to be treatment-emergent.

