5.3.1.1 Study treatment exposure

Study treatment start date is defined as the earliest study drug start date documented in the study drug administration or study drug log eCRF pages, as listed above.

The time of study treatment start (time of first exposure to treatment) is taken from the study drug administration eCRF, where the date is equal to the study treatment start date, if available.

The EOT date is defined as the latest study treatment end date, as recorded on the Study Drug Log eCRFs listed above.

The following exposure variables are derived:

Duration of Study Treatment (days) = EOT date - Study treatment start date + 1 day. Duration of Study Treatment is also derived in weeks (days divided by 7), months (days divided by 30.4375), and years (days divided by 365.25).

Duration of Study Treatment is categorized as follows: ≤ 24 weeks (168 days), > 24 weeks to ≤ 48 weeks (336 days), > 48 weeks to ≤ 72 weeks (504 days), > 72 weeks to ≤ 96 weeks (672 days), > 96 weeks to ≤ 120 weeks (840 days), > 120 weeks to ≤ 144 weeks (1008 days), > 144 weeks (1008 days).

‘Study treatment exposure, interruptions excluded’ equals the ‘Number of days with intake documented’ for a subject overall as defined as part of the compliance derivations described in Section 5.3.1.2.1.

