5.5.13 Other safety variables

5.5.13.1 Pulmonary function tests - Spirometry

Spirometry tests to assess pulmonary function will be performed at Visit 2 (Baseline), Visit 6 (Week 12), Visit 9 (Week 48) and every 48 weeks thereafter until Visit 17 (Week 144), Visit 18 (EOT), Visit 20 (FU), and at unscheduled visits (U1, U2, etc.) if clinically indicated. If applicable, spirometry tests will also be performed at the corresponding visits in the PTOP.

Spirometry tests will be conducted at site according to the ATS/ERS guidelines [Miller 2005a, Miller 2005b]. The best (largest) forced expiratory volume in 1 second (FEV₁), forced vital capacity (FVC) and peak expiratory flow (PEF) values from the three acceptable and repeatable tests will be recorded in the eCRF as absolute volume in liters and as flow in liters/second (rounded to two decimal places). These values may come from separate maneuvers. The FEV₁/FVC ratio will be derived from the FVC and FEV₁ values recorded in the eCRF.

Prior to database lock and unblinding, spirometry data are not transferred to any member of Actelion biostatistics as these data are considered to carry a moderate risk of potential unblinding. The following parameters are collected on the eCRF at each visit:

- FVC (L),
- FEV₁ (L),
- PEF (L/s).

The following variables are derived for analysis (predicted values based on Quanjer [Quanjer 1993]):

- FEV₁/FVC (%),
- Predicted normal FEV₁[L] for male subjects = $4.30 \times \text{height (m)} - 0.029 \times \text{age (years)}$ at study enrollment - 2.49;
- Predicted normal FEV₁[L] for female subjects = $3.95 \times \text{height (m)} - 0.025 \times \text{age (years)}$ at study enrollment - 2.60;
- Predicted normal FVC[L] for male subjects = $5.76 \times \text{height (m)} - 0.026 \times \text{age (years)}$ at study enrollment - 4.34;
- Predicted normal FVC[L] for female subjects = $4.43 \times \text{height (m)} - 0.026 \times \text{age (years)}$ at study enrollment - 2.89.

For the predicted normal values derivations above, age and height collected at study screening are used; also *age* is set to 25 years if age is between 18 and 25 years and a conversion factor of 0.9 must be multiplied to the predicted normal value if subject race is other than 'White'.

- Percent of the corresponding predicted normal value is also calculated for FEV₁[L] and FVC[L] as follows:

$$\text{Percent of the predicted value (\%)} = [\text{measured value}] \times 100 / [\text{predicted normal value}].$$

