11.4 Summaries by visit

Visit based safety and PD assessments are generally summarized according to the nominal visit. Except for Visit 18 (EOT/Week 156) in subjects prematurely discontinuing study treatment, Visit 19 (FU7d, Day 7 follow-up assessment for lymphocyte subset only), and Visit 20 (FU, Day 30 follow-up assessment). Those are derived following the rules below:

- Premature EOT visits are re-assigned following the visit windowing described in Section 11.3
- Day-7 follow-up assessment: Any assessment within EOT date + 6 days and EOT date + 15 days. If multiple assessments fall into that period, the one corresponding to the regular FU7d visit (Visit 19) is selected, if none of the multiple assessments corresponds to that visit, the one closest to EOT date + 7 days is selected, if there are two closest assessments, the later one is selected.
- Day-30 follow-up assessment: Any assessment within EOT date + 16 days and EOT date + 37 days. If multiple assessments fall into that period, the one corresponding to the regular FU visit (Visit 20) is selected, if none of the multiple assessments corresponds to that visit, the one closest to EOT date + 30 days is selected, if there are two closest assessments, the later one is selected.

In addition, the ‘Last on-treatment’ assessment is flagged. This is defined to be the latest assessment prior to or on EOT date + 1 day (last on treatment may come from a scheduled or an unscheduled visit).

Summaries by visit are presented by Baseline (derived), and further scheduled nominal visits up to Week 156 (irrespectively if conducted during PTOp or not), Last on-treatment, and derived Follow-up visits (FU7d, FU). Generally, by visit tables are tabulating the baseline and nominal and derived visits as follows:

- Baseline (Note: This is not a nominal visit but the derived baseline; see Section 5.5.1)
- Visit 4 - Week 2

- Visit 5 - Week 4
- Visit 6 - Week 12
- Visit 7 - Week 24
- Visit 8 - Week 36
- Visit 9 - Week 48
- Visit 10 - Week 60
- Visit 11 - Week 72
- Visit 12 - Week 84
- Visit 13 - Week 96
- Visit 14 - Week 108
- Visit 15 - Week 120
- Visit 16 - Week 132
- Visit 17 - Week 144
- Visit 18 - Week 156
- Last on-treatment (derived; see Section 5.5.1)
- Day-7 follow-up (derived) (lymphocyte subset only)
- Day-30 follow-up (derived)

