3.2 Efficacy / Endpoint

Condition	Type	Identifier	Source/Instructions	Additional information expected?	Important PD
FSIQ-RMS symptoms domain not assessable at EOS visit	M	PD_MM.156	Monitor PD e.g., not completed for at least 4 days		No

Visit 18 (EOT) not performed within 7 days after study drug discontinuation for a subject who completed the treatment period as per study protocol	M	PD_MM.261	Monitor PD / eCRF [Visit Summary] e.g., EOT visit performed out of time window	No
Visit 18 (EOT) not performed within 7 days after study drug discontinuation for a subject who prematurely discontinued study drug	M	PD_MM.262	Monitor PD / eCRF [Visit Summary] e.g., EOT visit performed out of time window	No
Visit 18 (EOT) not performed for a subject who completed the treatment period as per study protocol	M	PD_MM.314	Monitor PD / eCRF e.g., EOT visit not done	Yes
Visit 18 (EOT) not performed for a subject who prematurely discontinued study drug	M	PD_MM.315	Monitor PD / eCRF e.g., EOT visit not done	Yes

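### The 'Last on-treatment' rule has no lower date limit and stops at EOT + 1 day, so a pre-treatment or long out-of-date value (mainly spirometry) can carry an on-treatment label

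*SAP*

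**What the plan says.** Section 5.5.1 gives the rule as "Last on-treatment assessment: Last assessment prior to or on EOT date +1 day". Section 11.4 repeats it: "This is defined to be the latest assessment prior to or on EOT date + 1 day". Both add that the value may come from a scheduled or an unscheduled visit. Neither states an earliest date.

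The anchor is the last dose, not the visit. Section 5.3.1.1 says: "The EOT date is defined as the latest study treatment end date, as recorded on the Study Drug Log eCRFs listed above".

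The EOT visit has a + 7 day window in Table 3 (section 2.2). The deviation code list (Attachment 1, section 3.2) treats as a deviation only an EOT visit "not performed within 7 days after study drug discontinuation".

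Sections 9.9.3 (ECG), 9.9.4 (vital signs and weight), 9.9.5 (laboratory) and 9.9.6 (spirometry) limit by-visit summaries to treatment-emergent results from nominal scheduled visits. All four except the baseline, *Last on-treatment* and Day-30 follow-up rows from that limit.

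Spirometry is sparse. Section 5.5.13.1 schedules it at baseline, then "Visit 6 (Week 12), Visit 9 (Week 48) and every 48 weeks thereafter" to Week 144, at EOT and follow-up, and unscheduled if clinically indicated.

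**The concern.** A row labelled *Last on-treatment* should hold a value taken after the first dose and reasonably close to the last one. The rule as written guarantees neither. The treatment start date could have served as a lower limit, but the exemption in 9.9.3 to 9.9.6 removes it for this row. The upper limit of EOT + 1 can exclude a fully compliant EOT visit, and the rule then selects whatever came before, including a screening or baseline value.

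The row has some weight here. Section 5.1.5 expects no per-protocol treatment completers, and section 2 required subjects on treatment at termination to perform an EOT visit. For most subjects the final measurement is therefore an early EOT visit, and this is the row that would pool those final values across subjects.

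**Working it through.** **Inputs**
- Upper limit: EOT + 1 (5.5.1, 11.4). Lower limit: none.
- Compliant EOT visit days: EOT + 0 to EOT + 7 (Table 3; Attachment 1, section 3.2).
- Nominal day of Week w = 7w + 1 (Table 6). Spirometry at Weeks 12, 48, 96 and 144 falls on days 85, 337, 673 and 1009.
- Laboratory tests at Weeks 2, 4, 12 and every 12 weeks thereafter (5.5.12), i.e. days 15, 29, 85, 169 and so on.
- Assumptions: visits on nominal days, earlier scheduled visits counted only if on or before the last dose, no missing results, no unscheduled tests.

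**Step 1: visits missed by the cut.** Of the 8 permitted days (0 to 7), days 2 to 7 lie beyond EOT + 1, so 6 of 8 permitted days are missed. This counts calendar days; it does not estimate how many subjects are affected.

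**Step 2: fallback when the EOT visit is on EOT + 2 to + 7**, over every EOT day from 1 to 1092.

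| Measure | EOT days with only a pre-treatment value | Oldest on-treatment value selected |
|---|---|---|
| Spirometry | 1 to 84 | 672 − 337 = 335 days (335/7 = 47.9 weeks) |
| Laboratory | 1 to 14 | 168 − 85 = 83 days (83/7 = 11.9 weeks) |

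For spirometry stops between Week 12 and Week 48, the oldest value is 336 − 85 = 251 days (35.9 weeks). With the EOT visit on EOT + 1, neither problem arises. The ± 7 day visit windows can shift these ages slightly.

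**Step 3: whether another by-visit row shows the EOT result.** Take EOT day 350, EOT visit day 353, Week 48 result present.
- *Last on-treatment* cut: 350 + 1 = 351, so day 353 is excluded.
- Section 11.3 uses a premature EOT visit only where the scheduled result is missing. Week 48 (days 295 to 378) is already filled.
- Day-30 follow-up starts at 350 + 16 = 366.

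The result enters none of these columns. It does fall inside the treatment-emergent window, which ends at 350 + 15 = 365, so it still counts in the low-value table of 9.9.6.

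**Step 4: comparison within the SAP.** The on-treatment flag for EDSS (5.4.4.2) covers "EDSS assessments performed after study treatment start (date/time) and prior to EOT + 7 days". It has a lower limit and a longer tail, although read strictly it excludes day + 7 itself. Treatment-emergent safety data run to EOT + 15. The SAP gives no reason for the different limit here.

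**The case against.** Much of the case on the other side stands.

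- **Change from baseline.** Section 5.5.1 defines change as a post-baseline value minus baseline. A reader might infer that a baseline value in this row enters as a change of zero, so that if a share p of subjects is affected the mean change shrinks by a factor of 1 − p. The documents do not support that: under the definition such a record may have no change at all, and p is not given. What remains is that the pre-treatment value itself can be tabulated under an on-treatment label.
- **Purpose of the exemption.** It may exist only because this row admits unscheduled visits, and the spirometry bullet in 9.9.6 opens by referring to treatment-emergent values. However, the same bullet covers the baseline row, which cannot be treatment-emergent, so its opening word does not settle the matter.
- **Other parameters.** Hourly post-dose blood pressure and ECG on Day 1 normally supply a post-dose value, and laboratory tests are frequent. The pre-treatment fallback is mainly a spirometry issue.
- **Differential bias.** A reader might also infer that the arm with more toxicity stops is distorted most. This is not established. Subjects with respiratory problems are candidates for unscheduled spirometry and repeat testing, and those values count for this row.
- **The EOT + 1 limit.** It defensibly keeps off-drug values out of an on-treatment row. That justifies the upper limit, but not the missing lower one.
- **Frequency.** The + 7 days is an outer limit. Many EOT visits may fall on or next to the last dose.

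**Conclusion.** The concern holds as a narrow defect in a stated rule. As written, a pre-treatment value can be labelled *Last on-treatment*. This arises mainly for spirometry in subjects who stop before Week 12, have their EOT visit on EOT + 2 to + 7 (or no EOT result) and have no unscheduled test. For later stops under the same conditions, the value shown can be up to about 48 weeks old. These figures rest on nominal visit timing.

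The effect is confined to the descriptive *Last on-treatment* rows. Counts of treatment-emergent abnormalities run to EOT + 15 and still include the EOT visit, and all results are listed. The number of subjects affected cannot be derived from the SAP, and nothing in it fixes a size or direction of bias between arms. The efficacy analyses are not touched.

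**What to change.** In 5.5.1 and 11.4, define *Last on-treatment* as the last assessment after first study drug intake (baseline and pre-dose Day 1 values excluded) and on or before EOT + 1 day; missing if none. This takes one sentence in each section and a small programming change. Subjects without a qualifying value drop out of the row, so its N should be shown.

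The lower limit removes pre-treatment values but does not shorten the age of later ones. Optionally, keep EOT + 1 as the main rule and add, for spirometry only, a supportive row that uses the EOT visit (Visit 18) value if done by EOT + 7 days. The downside is that some of those values are up to 7 days off drug, so the row should be labelled accordingly. Neither change affects visit timing or treatment.
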